3.1.4 Dose Escalation Rules and Dose Staggering Approach

Dose staggering will be applied for all cohorts during dose escalation. The first dose of the first patient will be administered at least 2 weeks before the first dose of the remainder of the cohort. After the review of AEs, dosimetry reports, vital signs, and electrocardiograms (ECGs) collected over 2 weeks, the remaining 2 patients of the cohort may receive the same dose level. Following completion of the initial safety assessments for the sentinel patient, the decision to proceed with the remaining patients in that cohort will be discussed and mutually agreed upon between the Investigator (or his/her designee) and the Sponsor. The decision of whether to escalate to the next dose will be formally confirmed by the Sponsor.

The proposed minimum 2 weeks between the sentinel patient and the remainder of the cohort is deemed sufficient as each dose of the cycle is a single IV administration, and it is expected that the most severe and acute reactions will occur during or soon after the infusion. Based on animal studies, potential side effects are expected to be related to high activity levels in the kidneys, that will decline rapidly after ending the IV infusion.

At each dose level, after completion of 1 cycle (2 doses) of CAM-H2 administration in at least 3 patients, each Investigator will provide a comprehensive Investigator Safety Report for his/her patients including (but not limited to) the following content:

- Relevant information on patients' demographics, characteristics, medical history, physical examination, and concomitant medications;
- List of all AEs, including severity, time of onset related to study drug administration, and duration, clearly highlighting serious adverse events (SAEs) and relatedness and causality of all AEs;
- Any clinically significant out of range clinical laboratory test results (as assessed by the Investigator);
- Neurological examination results including clinical significance for abnormal findings;
- ECG and vital sign results including clinically significant abnormal values; and
- Statement of the Principal Investigator's recommendation regarding dose decision.

Escalation to the next higher dose will only take place after review of the Investigator Safety Reports from the previous dose levels by the respective Investigators, in consultation with the Sponsor's representative (called hereafter the Safety Review Committee [SRC]). Dose escalation

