will be based on dosimetry and emerging safety and tolerability data as defined by AEs, laboratory results, ECGs, and vital signs. Other parameters of interest will be considered ad hoc.

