3.1.4.1 Definition of dose-limiting toxicities

DLTs are defined as toxicities occurring **only** within Cycle 1 (ie, the approximately 12-week [84-day] period that includes 2 administrations of the study drug given 4 weeks apart [including the 4-week Safety Follow-Up Period after Dose 1]). DLTs include ≥ 1 of the following:

- Study drug-related SAE in at least 1 patient in 1 cohort;
- Severe study drug-related AE in at least 2 patients in 1 cohort;
- Any death not clearly due to the underlying disease or extraneous causes;
- Development of severe renal failure (estimated glomerular filtration rate [eGFR] <30 mL/min) or a drop of >40 mL/minute in eGFR;
- Any seizure activity that is considered to be study drug-related;
- Grade 3+ thrombocytopenia with bleeding;
- Recurrent (defined in this study as occurring after >1 dose of CAM-H2 during Cycle 1) Grade 3 or 4 thrombocytopenia;
- Grade 4+ neutropenia or thrombocytopenia >7 days;
- Recurrent (defined in this study as occurring after >1 dose of CAM-H2 during Cycle 1) Grade 3 or 4 anemia and/or neutropenia;
- Recurrent (defined in this study as occurring after >1 dose of CAM-H2 during Cycle 1) Grade 3 or 4 non-hematological toxicities as listed in the Common Terminology Criteria for Adverse Events (CTCAE) version 5.0;
- An alanine aminotransferase (ALT) or aspartate aminotransferase (AST) $>3 \times$ upper limit of normal (ULN) accompanied by a total bilirubin of $>2 \times$ ULN (Hys Law);
- Grade 3 or 4 fatigue for >1 week;
- Grade 3 or 4 electrolyte abnormalities that last >72 hours or any Grade 3 or 4 electrolyte abnormalities associated with clinical signs and symptoms of any duration;
- For patients with hepatic metastases, AST or ALT $>8 \times$ ULN or AST or ALT $>5 \times$ ULN for ≥ 14 days;
- An absorbed dose to the kidneys >23 Gy;
- An absorbed dose to the bone marrow >2 Gy; or
- Other clinically significant changes in vital signs, clinical laboratory tests, ECGs, or other safety parameters deemed as a significant safety concern by the Investigator.

All AEs of the specified grades will count as DLTs, except those that are clearly and incontrovertibly due to disease progression or extraneous causes.

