3.1.4.2 Dose escalation rules

DLTs will determine the progression/escalation with the following rules:

- If 0 out of 3 patients experience a DLT, all patients will proceed to the next higher dose level;
- If 1 out of 3 patients experiences a DLT, the same dose will be given to 3 new patients:
 - If 0 of the 3 new patients experience a DLT, all patients will proceed to the next higher dose level; and/or
 - If 1 or more of the 3 new patients experiences a DLT (≥ 2 of the 6 patients) this dose will become the MTD + 1.
- If ≥ 2 out of 3 patients experience a DLT, the MTD has been exceeded and a lower dose should be tested between this dose and the previous dose level;
- Once the MTD + 1 has been established, 3 additional patients will be exposed to the dose below the MTD + 1; and
- If the MTD + 1 is not reached, 3 additional patients will be exposed to the highest dose.

Within the planned dose range, a dose lower than the next planned dose may also be tested, depending on emerging safety, tolerability, and/or other relevant data, such as dosimetry or PD. If the highest planned dose level is found to be safe and tolerable, also considering the PD data, additional higher doses may be added by amendment.

A period of at least 4 weeks will be maintained between 2 consecutive cohorts.

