3.1.5 Stopping Rules, Dose Modifications, and Missed Doses

3.1.5.1 Stopping rules

During the dose escalation phase, the SRC will meet to decide on the continuation of dosing after the completion of 1 full treatment cycle in at least 3 patients at each dose level. During the dose expansion phase, the SRC will formally meet after the completion of 1 full treatment cycle in every 9 patients to review all emerging safety and tolerability data. All data must be available to the SRC ≤ 3 weeks after the last dose in the cohort. Additional details are described in the SRC Charter.

Safety and tolerability data; however, will be reviewed on an ongoing basis by the Medical Monitor, and stopping rules will be applicable starting with dosing of the first sentinel patient. SRC decisions will be based on the following:

- If a study drug-related SAE occurs in 1 patient or if a study drug-related severe AE occurs in 2 patients in the same cohort, the dosing in the study should be temporarily stopped in order to review additional safety data. If after review of the additional data, the study drug-relatedness assessment changes, the study can resume without substantial amendment;
- If 2 patients in a cohort experience a DLT that is related to CAM-H2 administration, dosing will be stopped until resolution of the DLT. Doses can be adapted as per the modification schemes in [Section 3.1.5.2](#);

- If at least 1 DLT is reported, the SRC recommendation will depend on the DLT profile (ie, identical DLTs in different patients), the frequency and severity of DLTs in the same patient, and the recommendation made by the Investigator; and
- If no DLT is reported, the planned dose escalation may proceed with the next cohort or phase, unless the Investigator has any other safety concerns.

All decisions will be documented in writing and communicated to the study team in a timely manner before dosing in the next cohort can start.

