6.2.2.2 Visit 4 (Week 1)

The following procedures will be performed at Visit 4 (Week 1):

- Assess AEs;
- Perform physical examination;
- Measure vital signs;
- Perform clinical laboratory tests;

Note: Clinical laboratory tests should be performed prior to any imaging.

- Perform triplicate 12-lead ECGs;
- Perform urinalysis for kidney biomarkers and for microscopic evaluation of sediment; and
- Perform a planar WB scan and a SPECT/CT scan 168 (± 24) hours after study drug administration.

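### In escalation Cycle 1, no written rule checks a patient's own Dose 1 kidney dose against the 23 Gy limit before Dose 2, although the last Dose 1 scan is about 3 weeks earlier

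*Combined protocol and SAP*

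**What the plan says.** **The limit.** Section 3.1.4.1 confines DLTs to Cycle 1, which contains two administrations 4 weeks apart, and lists "An absorbed dose to the kidneys >23 Gy". It does not say outright that the 23 Gy is the sum of the two doses. Sections 1.3.2 (kidney dose estimated for 2 × 200 mCi) and 3.1.1.2 (cumulative kidney dose) make that the likelier reading.

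**The data.** Section 3.1.1.3 and Table 1 schedule planar and SPECT/CT scans at 5, 24, 48 and 168 h after each Cycle 1 dose. For Dose 1 the series ends at Visit 4: "Perform a planar WB scan and a SPECT/CT scan 168" hours after administration. Dose 2 is given at Visit 7, Week 4 (6.2.2.5).

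**Where dosimetry is used.**
- A cumulative kidney dose below 23 Gy is a condition for starting Cycles 2, 3 and 4 (3.1.1.2, 6.2.3.10).
- The sentinel review, "After the review of AEs, dosimetry reports, vital signs, and electrocardiograms (ECGs) collected over 2 weeks", releases the other patients of the cohort (3.1.4).
- Escalation between levels "will be based on dosimetry and emerging safety and tolerability data" (3.1.4), and within the planned range "a dose lower than the next planned dose may also be tested" (3.1.4.2). Level 4 is optional and depends partly on dosimetry (5.1, Table 3).

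**Discretion.** The DLT list ends with "other safety parameters deemed as a significant safety concern by the Investigator". Section 3.1.5.1 adds: "Safety and tolerability data; however, will be reviewed on an ongoing basis by the Medical Monitor". Kidney absorbed dose is a listed safety variable (Section 8), and Section 4.3 allows discontinuation of a patient exposed to substantial risk.

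**The concern.** The protocol names the kidney as the predicted dose-limiting organ, sets an absorbed-dose limit for it, and measures each escalation patient's kidney dose well before Dose 2. It then prescribes no use of that measurement for that patient's Dose 2. A patient whose Dose 1 result already projects past 23 Gy would, if the text is simply followed, receive full Dose 2 and be recorded as a DLT afterwards.

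The plan uses this kind of check elsewhere. A negative distribution scan after Dose 1 ends that patient's treatment (Table 1, footnote 1), and measured kidney dose governs later cycles. No reason is given for leaving the check out between the two Cycle 1 doses.

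There is a second consequence for the 3 + 3 count. If someone uses discretion and reduces or holds Dose 2, the measured cycle dose may stay below 23 Gy and no DLT is recorded. One such patient among three turns a 1/3 result (treat three more) into 0/3 (escalate). The replacement rules in 3.1.1.2 do not mention a Dose 2 withheld for projected kidney dose, and Section 4.3 lets the sponsor replace withdrawn patients.

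**Working it through.** **Inputs.** Predicted kidney coefficient 34.9 mGy/mCi, with amino acids, male, extrapolated from non-human primates (1.3.2). Limit 23 Gy (1.3.2, 3.1.4.1). Activities per dose 50, 100, 150 and 200 mCi (5.1, Table 3). Administered activity within ±10% of nominal (3.1.1.2). Last Dose 1 scan 168 ± 24 h. Dose 2 at Week 4, ± 3 days (Appendix A, Table 7).

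**Step 1: reproduce the plan's figures.** 23 / 0.0349 = 659 mCi (plan: 659). 400 × 0.0349 = 13.96 Gy (plan: 14 Gy). Both agree.

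**Step 2: where each level crosses 23 Gy.** Predicted cycle dose = 2 × mCi per dose × 0.0349. Crossing coefficient = 23,000 / (2 × mCi per dose). Multiple = crossing coefficient / 34.9.

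| Level | mCi per dose | Predicted cycle dose (Gy) | Crossing coefficient (mGy/mCi) | Multiple of prediction |
|---|---|---|---|---|
| 1 | 50 | 3.49 | 230 | 6.59 |
| 2 | 100 | 6.98 | 115 | 3.30 |
| 3 | 150 | 10.47 | 76.7 | 2.20 |
| 4 | 200 | 13.96 | 57.5 | 1.65 |

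With both Level 4 doses at +10%: 23,000 / 440 = 52.3 mGy/mCi, or 1.50 times prediction. At equal activities the Level 4 warning sign is a Dose 1 kidney dose above 23 / 2 = 11.5 Gy.

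**Step 3: time available.** The last scan falls 6 to 8 days after Dose 1 and Dose 2 falls 25 to 31 days after it. Nominal gap: 28 − 7 = 21 days. Tightest: 25 − 8 = 17 days. Section 3.1.1.3 requires images to be sent within 48 h of acquisition but sets no deadline for a dosimetry result.

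**Step 4: look for a rule that acts before the same patient's Dose 2.**
- Dose modification (3.1.5.2): the renal trigger is eGFR, and no absorbed-dose trigger is listed.
- Visit 6 and Visit 7 procedures (6.2.2.4, 6.2.2.5): no dosimetry check.
- Sentinel review (3.1.4): governs the other patients and states no Gy threshold.
- Safety Review Committee (SRC, 3.1.5.1): meets "after the completion of 1 full treatment cycle in at least 3 patients at each dose level", so after both doses.
- DLT stopping rule (3.1.5.1): needs two patients in a cohort.
- The 23 Gy condition (3.1.1.2, 6.2.3.10): applies to later cycles only.

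None of these acts on the patient's own Dose 1 kidney dose.

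**Step 5: would the plan's existing 50% step be enough?** At Level 4, 200 + 100 = 300 mCi, and 23,000 / 300 = 76.7 mGy/mCi, a Dose 1 kidney dose of 15.3 Gy. Example with an assumed 65 mGy/mCi: Dose 1 gives 13.0 Gy, the full cycle 26.0 Gy, and a cycle with a 50% Dose 2 gives 19.5 Gy.

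**The case against.** The strongest reply is that competent people already hold the result. The Investigator and sponsor review the sentinel's dosimetry at about 2 weeks, before that patient's own Dose 2. The Medical Monitor reviews safety data continuously, and the Investigator can declare a DLT or withdraw the patient. Laboratory tests and kidney biomarkers are also collected at Visits 4, 5 and 6 and before Dose 2. This stands. A reader might infer that nothing could stop Dose 2, and the documents do not support that. But the discretion has no threshold, timing or report date, and the laboratory tests and biomarkers show injury, not absorbed dose.

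Second, the mean prediction is 14 Gy, and dosimetry from at least nine earlier patients (three at each of three levels) will inform whether Level 4 opens or an intermediate dose is chosen. This also stands, and it confines the issue mainly to Level 4. Earlier patients can reveal a high average or a wide spread, but they cannot identify the next outlier.

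Third, a reader might attach a probability to exceedance. The documents do not support one. The ±2 beside 34.9 belongs to the primate extrapolation. Read as between-patient spread (about 6%), it makes exceedance effectively zero. Assumed lognormal CVs of 20% to 50% give 0.44% to 9.80% per Level 4 patient, more than a twentyfold range set entirely by the assumption. The earlier human study in Section 1.2 is described without kidney dose values.

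Fourth, projecting Dose 2 from Dose 1 assumes that they behave alike, and Section 2.2 makes intra-patient dosimetry a question under study. That is a real cost of the fix. Finally, the SRC Charter and Imaging Review Charter were not available and may contain a check. If so, a cross-reference would do, though a rule on giving a patient's next dose belongs in the protocol.

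**Conclusion.** The gap is real and limited. In this protocol, full Dose 2 is the written default even for a patient whose own Dose 1 scans project a Cycle 1 kidney dose above 23 Gy. The thresholds assume that kidney dose is proportional to activity and that 23 Gy is the sum over both doses. They need no assumption about spread. A reader might infer that the planned doses are expected to breach the limit. They are not: every level's mean prediction is below 23 Gy, and a breach requires a patient at 1.65 times prediction at Level 4 (1.50 with both activities at +10%) or 2.20 times at Level 3. The case therefore rests on a foreseeable individual excess that data already collected could show, and on the undefined DLT status if Dose 2 is changed. It does not rest on an estimated frequency. The point should be settled before Level 4 opens.

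**What to change.** 1. In 3.1.4.1, state that 23 Gy is the sum of the kidney doses from both Cycle 1 administrations.
2. In 3.1.5.2 and the escalation Visit 7 procedures, require the Dose 1 kidney result to be reported before Dose 2, for example by Visit 6 (Week 3). Also require Dose 1 Gy + (Dose 1 Gy/mCi × planned Dose 2 mCi) to be at or below 23 Gy. Otherwise reduce Dose 2 to stay within the limit, or hold it. The existing 50% step suffices up to 76.7 mGy/mCi at Level 4.
3. In 3.1.1.2, state that such a patient is not replaced. In 3.1.4.2, state that a projected full-dose Cycle 1 kidney dose above 23 Gy counts as a DLT for the 3 + 3 decision, so that reducing Dose 2 does not mask it. Give the projected value to the SRC.

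**Cost.** No new scans. Dosimetry must, however, be reported before Dose 2 for every escalation patient, not only sentinels. Some reductions will prove unnecessary: with Dose 1 at 13 Gy (projected 26), a full Dose 2 would have stayed within the limit had it delivered at most 10 Gy, at least 23% less than Dose 1 (1 − 10/13). Counting projections as DLTs may make the MTD slightly conservative if Dose 2 would have delivered less than Dose 1.

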3.1.4.2 Dose escalation rules

DLTs will determine the progression/escalation with the following rules:

- If 0 out of 3 patients experience a DLT, all patients will proceed to the next higher dose level;
- If 1 out of 3 patients experiences a DLT, the same dose will be given to 3 new patients:
 - If 0 of the 3 new patients experience a DLT, all patients will proceed to the next higher dose level; and/or
 - If 1 or more of the 3 new patients experiences a DLT (≥ 2 of the 6 patients) this dose will become the MTD + 1.
- If ≥ 2 out of 3 patients experience a DLT, the MTD has been exceeded and a lower dose should be tested between this dose and the previous dose level;
- Once the MTD + 1 has been established, 3 additional patients will be exposed to the dose below the MTD + 1; and
- If the MTD + 1 is not reached, 3 additional patients will be exposed to the highest dose.

Within the planned dose range, a dose lower than the next planned dose may also be tested, depending on emerging safety, tolerability, and/or other relevant data, such as dosimetry or PD. If the highest planned dose level is found to be safe and tolerable, also considering the PD data, additional higher doses may be added by amendment.

A period of at least 4 weeks will be maintained between 2 consecutive cohorts.

3.1.5 Stopping Rules, Dose Modifications, and Missed Doses

3.1.5.1 Stopping rules

During the dose escalation phase, the SRC will meet to decide on the continuation of dosing after the completion of 1 full treatment cycle in at least 3 patients at each dose level. During the dose expansion phase, the SRC will formally meet after the completion of 1 full treatment cycle in every 9 patients to review all emerging safety and tolerability data. All data must be available to the SRC ≤ 3 weeks after the last dose in the cohort. Additional details are described in the SRC Charter.

Safety and tolerability data; however, will be reviewed on an ongoing basis by the Medical Monitor, and stopping rules will be applicable starting with dosing of the first sentinel patient. SRC decisions will be based on the following:

- If a study drug-related SAE occurs in 1 patient or if a study drug-related severe AE occurs in 2 patients in the same cohort, the dosing in the study should be temporarily stopped in order to review additional safety data. If after review of the additional data, the study drug-relatedness assessment changes, the study can resume without substantial amendment;
- If 2 patients in a cohort experience a DLT that is related to CAM-H2 administration, dosing will be stopped until resolution of the DLT. Doses can be adapted as per the modification schemes in [Section 3.1.5.2](#);

- If at least 1 DLT is reported, the SRC recommendation will depend on the DLT profile (ie, identical DLTs in different patients), the frequency and severity of DLTs in the same patient, and the recommendation made by the Investigator; and
- If no DLT is reported, the planned dose escalation may proceed with the next cohort or phase, unless the Investigator has any other safety concerns.

All decisions will be documented in writing and communicated to the study team in a timely manner before dosing in the next cohort can start.

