 - Cycle 2 (to begin 2 weeks after the Cycle 2 eligibility assessment for patients with CB during Cycle 1, as long as the cumulative kidney dose remains <23 Gy [based on the dosimetry results during Cycle 1 of dose escalation])
 - Dose 1 and Safety Follow-Up Period: Week 0 to Week 3
 - Dose 2 and Safety Follow-Up Period: Week 4 to Week 11 (EOT Visit)
 - Long-term follow-up period

One treatment cycle is defined as the timeframe of approximately 12 weeks (84 days) that includes 2 administrations of the study drug given 4 weeks apart (including the 4-week Safety Follow-Up Period after Dose 1 and the Safety Follow-Up Period after Dose 2, up to Visit 11) (see [Appendix A](#)).

However, if a patient misses a dose of study drug due to study drug production problems or due to other circumstances (in certain cases), the interval between doses may be extended up to 6 weeks (Cycles 1 and 2 of both dose escalation and dose expansion phases) or up to 12 weeks (Cycles 3 and 4 of the dose escalation phase) (see [Section 3.1.5.3](#)).

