Staggered dosing will be applied for all cohorts during dose escalation. The first dose of the first patient of each cohort will be administered at least 2 weeks before the first dose of the next 2 patients (sentinel dosing). Once the MTD or RDP2 has been established, 3 additional patients will be enrolled to receive the MTD or RDP2. The patients treated at the MTD or RDP2 in the dose escalation phase will be included in the readout for efficacy. The dose escalation will be done via increases of the nominal activity of CAM-H2 in cohorts of 3 to 6 patients until approximately 15 (or a maximum of 18) patients have been dosed. The actual dose levels administered to the patient can have a tolerance window of $\pm 10\%$ of the prescribed nominal activity.

Dose escalation will be decided based on a review of all the available safety data obtained after completion of Cycle 1 (ie, after 2 IV administrations) of each dose level. If a patient is not able to complete a full cycle due to AEs related to study drug administration, he/she will not be replaced, and the dose escalation rules will be followed.

In the instance that a patient is not able to complete a full cycle due to AEs not related to study drug administration or due to a negative PD distribution scan, he/she will be replaced to ensure safety data spanning a full treatment cycle can be considered for dose escalation.

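### The SRC data deadline (3 weeks after the last dose, about Week 7) falls about 5 weeks before the 84-day cycle and DLT window end, and completion of Cycle 1 can be read in two ways

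*Combined protocol and SAP*

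**What the plan says.** Section 3.1.5.1 has the SRC decide on continued dosing in the escalation phase "after the completion of 1 full treatment cycle in at least 3 patients at each dose level". The same paragraph adds "All data must be available to the SRC ≤ 3 weeks after the last dose in the cohort" and refers to the SRC Charter for further detail. The Synopsis repeats both sentences under Stopping Rules. Section 3.1.5.1 then lets escalation go ahead when no DLT has been reported, unless the Investigator has another safety concern.

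Section 3.1 gives the only formal definition of a cycle. It is about 12 weeks or 84 days, contains two doses 4 weeks apart, and includes "the Safety Follow-Up Period after Dose 2, up to Visit 11". Section 3.1.4.1 restricts DLTs to Cycle 1, described as "the approximately 12-week [84-day] period that includes 2 administrations of the study drug given 4 weeks apart".

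Two other sections describe completion by the number of doses. Section 3.1.1.2 bases escalation on safety data "obtained after completion of Cycle 1 (ie, after 2 IV administrations) of each dose level". Section 3.1.4 asks for the Investigator Safety Reports "after completion of 1 cycle (2 doses) of CAM-H2 administration in at least 3 patients". Yet Section 3.1.1.2 also replaces patients who cannot finish the cycle because of unrelated adverse events or a negative distribution scan, and gives its reason as "to ensure safety data spanning a full treatment cycle can be considered for dose escalation".

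**The concern.** The SRC is asked to act on full-cycle data, but the date by which it must hold all data comes well before a full cycle has been observed in the last-dosed patient. The sections do not agree on what a completed Cycle 1 is, so SRC members and sites could follow different rules.

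What is at stake is the observation on which DLT-based escalation rests. Visits 10 and 11 both include clinical laboratory tests and urinalysis (Sections 6.2.2.8 and 6.2.2.9), from which renal, hepatic and hematological DLTs are read. Three DLT criteria in Section 3.1.4.1 concern recurrent toxicity, defined as occurring after more than one dose in Cycle 1, so they can be met only after Dose 2. That is the part of the cycle the deadline cuts short.

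**Working it through.** **Inputs**
- SRC data deadline: 3 weeks = 21 days after the last dose (Section 3.1.5.1).
- Last dose: taken as Cycle 1 Dose 2 of the last-dosed patient. This is an assumption; the text does not say.
- Dose 2: Week 4, so 28 days after Dose 1 (Section 3.1.1.2).
- Cycle and DLT window: 84 days (Sections 3.1 and 3.1.4.1).
- Visits after Dose 2, with Dose 2 as D1 (Appendix A, Table 7): Visit 8 at D8 (±3), Visit 9 at D15 (±3), Visit 10 at D29 (+7), Visit 11 at D50 (±7).
- Dose 2 may be up to 6 weeks (42 days) after Dose 1, and later visits follow its actual date (Section 3.1.5.3).

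**1. The plan's own figure.** Weeks 0 to 11 inclusive are 12 weeks, and 12 × 7 = 84 days. Visit 11 is nominally 28 + 49 = 77 days after Dose 1, and its +7 window reaches 84. So the 84 days agree with a cycle that runs to Visit 11.

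**2. The deadline.** 28 + 21 = 49 days after Dose 1, or Week 7. Remaining: 84 − 49 = 35 days (5 weeks; 35/84 = 42%). If Dose 1 is called Day 1, Dose 2 is Day 29, the deadline is Day 50, and 84 − 50 = 34 days remain (34/84 = 40%). The two results differ only in day counting.

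**3. Visits against the deadline** (days after Dose 2, minus 21)

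| Visit | Days after Dose 2 | Against the deadline |
|---|---|---|
| 8 | 4 to 10 | 17 to 11 days before |
| 9 | 11 to 17 | 10 to 4 days before |
| 10 | 28 to 35 | 7 to 14 days after |
| 11 | 42 to 56 | 21 to 35 days after |

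No permitted visit window brings Visit 10 or Visit 11 inside the deadline.

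**4. Late Dose 2.** With Dose 2 at 42 days, the deadline is 42 + 21 = 63. Visit 10 is then at 70 to 77 days and Visit 11 at 84 to 98 days after Dose 1, so again 7 to 14 and 21 to 35 days past the deadline. The visit gaps do not change. The unobserved part of the window is 84 − 63 = 21 days if its end is fixed at 84 days, or 35 days if it moves with Dose 2; the text does not say which.

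**5. Time after Dose 2.** On the nominal schedule 84 − 28 = 56 days follow Dose 2. The deadline covers 21 of them and leaves 35 (35/56 = 62.5%).

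**6. The two readings of completion**
- The 84-day cycle up to Visit 11 (Section 3.1): the SRC decides after the window closes, but the deadline demands all data before they exist.
- Two doses given (one reading of Sections 3.1.1.2 and 3.1.4): trigger and deadline are compatible. But the absence of a reported DLT could then be judged with the last-dosed patient's window still open, against the aim in Section 3.1.1.2 of safety data over a whole cycle.

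**7. Other meanings of last dose.** Dose 1 of the last patient would put the deadline at 21 days (Week 3), before Dose 2. The last dose in any cycle would detach it from the Cycle 1 decision, because patients may receive up to 4 cycles. Neither removes the conflict.

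**The case against.** The strongest reply is that a latest date for data is not a date for a decision. Section 3.1.5.1 sets the meeting separately, after a full cycle. The only formal definition of a cycle is 84 days, and the escalation rules count DLTs defined over that period. The phrases about two doses can be read as saying what a cycle contains, not when it ends. On that view the SRC decides after the window closes and the deadline sentence is merely badly worded.

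Much of this stands. A reader might infer that the SRC is told to decide at Week 7; no text says so, and the SRC Charter, which may settle the timing, is not available. A reader might also infer that escalation becomes more likely or that the MTD or RDP2 is biased. The documents do not support that: they give no DLT onset times, and Section 3.1.4 expects the most severe and acute reactions at or soon after infusion. Nor do they establish that the effect is nil.

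There are real safeguards: ongoing Medical Monitor review, stopping rules from the first sentinel patient, the 2-week stagger, Investigator Safety Reports, formal Sponsor confirmation, and at least 4 weeks between cohorts. That last interval has no stated start or end point, so it cannot be converted into days of DLT window covered. The absorbed-dose DLTs are not affected, because the last Cycle 1 dosimetry scan is 168 (±24) hours after Dose 2.

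What the reply does not remove is the clash itself. Full-cycle data cannot be supplied before Visits 10 and 11 take place. The explanatory bracket in Section 3.1.1.2 gives the two-dose reading real support. A charter cannot make the protocol's own sections agree.

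**Conclusion.** The point holds as an internal contradiction: the rule is wrong as written, not merely short of detail. For the last-dosed patient the deadline precedes two of the four safety visits after Dose 2, and about 5 of the 12 weeks of the DLT window on the nominal schedule. The visit gaps hold for any permitted Dose 2 date; the 5-week figure assumes Dose 2 on time. Both rest on taking the last dose as Cycle 1 Dose 2 of the last-dosed patient.

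Escalation before that patient's window closes is a possibility on the two-dose reading only. No effect on the chance of escalation, the MTD or the RDP2 is estimated in either direction. Confidence is high for the textual clash and limited for its practical consequence. It should be fixed because it bears on patient safety and the remedy is cheap.

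**What to change.** Reconcile Sections 3.1, 3.1.1.2, 3.1.4, 3.1.4.1 and 3.1.5.1 and the matching Synopsis text, so that:
- one definition of a completed Cycle 1 applies throughout;
- the dose from which the SRC data deadline is counted is named;
- the data deadline, the SRC decision and the DLT window agree with one another.

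The timing is for the sponsor to choose, and no dose, escalation or stopping rule is proposed here. The SRC Charter should be checked against the result.

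The cost is amendment wording and no extra patients. Depending on the timing chosen, each escalation decision would come between zero and about 5 weeks later (35 days / 7).
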